16.3.2 Guidance on monitoring Participants with infections

All infections that develop during the study will be reported as AEs on the respective AE eCRF pages. Treatment and additional evaluations will be performed at discretion of the Investigator.

The Investigator should remind the participant of the risk of infections and instruct them to report any symptoms of infections promptly to the Investigator. The participants must also be reminded to always carry their participant Information Card (with site contact information and which identifies them as participants in a clinical study with investigational and control agents with potential immunosuppressive effects) and to show this to any local healthcare provider they may consult and ask that the Investigator be contacted.

In the case of suspected or confirmed serious (CTCAE, Grade 3-4) or atypical infection, study drug interruption should be considered. The Investigator should inform the Novartis Medical Advisor and/or a CTT member of any such cases.

When evaluating a participant with a suspected infection, the most sensitive tests available should be used (i.e. that directly detect the pathogen, as with polymerase chain reaction).

The Investigator should consider early treatment with specific antimicrobial therapy based on clinical diagnosis or suspicion thereof in consultation with infectious disease experts, as appropriate. The Investigator should inform the Novartis Medical Advisor and CTT of any such cases.

Investigators should consider the added immunosuppressive effects of corticosteroid therapy for treatment of MS attack/relapse and increase vigilance regarding infections during such therapy and in the weeks following administration.

In participants with known malignancies treated with ofatumumab, cases of fatal hepatitis B virus (HBV) reactivation and fatal infection due to hepatitis B in participants who have not been previously infected have occurred (refer to local Arzerra® prescribing information). The MS participants enrolled in the study who are at potential risk of HBV reactivation (e.g. Participants with evidence of prior HBV infection (antibody to hepatitis B surface antigen (anti-HBc) positive and Hepatitis B surface antigen (HBsAg) negative) and whose HBV deoxyribonucleic acid (DNA) test is negative at Screening, should be closely monitored for signs of active HBV infection or reactivation during the study. In participants with suspicion of HBV infection (active/reactivation), laboratory testing for HBV should be done. For participants who show evidence of hepatitis B infection (HBsAg positive [regardless of antibody status] or HBsAg negative but anti-HBc positive), the Investigator is advised to consult with physicians with expertise in managing hepatitis B regarding monitoring and consideration for HBV antiviral therapy.

In participants who develop reactivation of HBV while receiving study drug, immediately discontinue study drug and institute appropriate treatment and follow-up.

16.3.3 Guidance on immunization

The safety of and ability to generate a primary or anamnestic (recall) response to immunization with live, live-attenuated or inactivated vaccines during ofatumumab treatment has not been investigated. The response to vaccination could be impaired when B-cells are depleted.

It is recommended that the Investigator review the participant's immunization history as part of the initial Screening procedure for a participant being considered for treatment with ofatumumab.

Administration of live or live-attenuated vaccines must be avoided during and after treatment with ofatumumab and until B-cell counts are normalized.

There is presently no contraindication for the use of an inactivated, viral-vector-, or mRNA based Sars-CoV-2 vaccine in patients who are immunocompromised. However, different Sars-CoV-2 vaccines may have various mechanisms of action and different associated potential risks. Please review local prescribing information of any specific Sars-CoV-2 vaccine and comply with local prescribing information requirements for specific contraindications and special warnings and precautions for use. Vaccination against Sars-CoV-2 should be considered on a case-by-case basis at the discretion of the treating physician taking into account the individual benefit-risk assessment and local vaccination recommendations

16.3.4 Guidance on monitoring of Participants with low immunoglobulin levels

During the study, the immunoglobulin levels (IgG and IgM) will be measured according to the schedule in [Table 8-1](#) and [Table 8-2](#). If IgG levels were to drop below 300mg/dL ([Agarwal and Cunningham-Rundles 2007](#)), study drug treatment should be interrupted and the Investigator should evaluate participant for any potential infections and monitor on a regular basis. Immunoglobulin substitution therapy as per local medical practice is allowed. In case of treatment interruption, re-initiation of the study drug can only be considered once the immunoglobulin levels are back within normal limits.

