6.2 Other treatment(s)

6.2.1 Concomitant therapy

The Investigator should instruct the participant to notify the study site about any new medications he/she takes after study enrollment. All medications, procedures, and significant non-drug therapies (including physical therapy and blood transfusions) administered after the participant was enrolled into the study must be recorded on the appropriate Case Report Forms.

Each concomitant drug must be individually assessed against all exclusion criteria/prohibited medication. If in doubt, the Investigator should contact the Novartis medical monitor before enrolling a participant or allowing a new medication to be started. If the participant is already enrolled, contact Novartis to determine if the participant should continue participation in the study.

If a participant is receiving dalfampridine (Ampyra[®]/Fampyra[®]) concomitantly with study treatment, the participant should have been on a stable dose at least 30 days prior to first study drug administration and remain on that dose throughout the study wherever possible.

Premedication prior to subcutaneous injection

Premedication is not required. Premedication with acetaminophen and/or antihistamines (or equivalent) is optional and may be administered at the discretion of the Investigator. For the first injection of treatment period (Day 1), the addition of premedication with steroids (methylprednisolone 100 mg iv or equivalent) is an additional consideration. If Investigators choose to administer premedication, it should be administered 30 to 60 minutes prior to study drug injection.

Any administrations of premedication must be recorded in the appropriate CRF.

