6.2.2 Prohibited medication

Use of the treatments displayed in [Table 6-1](#) is NOT allowed in combination with study drug, due to increased risk of immunosuppression and confounding of efficacy evaluations.

Exclusionary medications for study eligibility are listed in the exclusion criteria ([Section 5.2](#)). Use of excluded medications is not allowed while the participant is on study medication.

Table 6-1 Prohibited medication

Medication	Action taken
Immunosuppressive/chemotherapeutic medications (including herbal) or procedures, including but not limited to cyclosporine, azathioprine, leflunomide, methotrexate, cyclophosphamide, mitoxantrone, lymphoid irradiation and hematopoietic stem cell transplantation	Discontinue study drug, increase vigilance regarding infections. NOTE: Restarting study drug in participants exposed to these medications is not permitted.
Monoclonal antibodies targeting the immune system, including but not limited to natalizumab, alemtuzumab, daclizumab and B-cell depleting agents under investigation, such as but not limited to ublituximab and obinutuzumab	Discontinue study drug, increase vigilance regarding infections. NOTE: Restarting study drug after exposure to B-cell depleting agents is not permitted. For others only after consultation with the Sponsor.
Any other immunomodulatory or disease-modifying MS treatment, including but not limited to fingolimod, interferon beta, glatiramer acetate, dimethyl fumarate, intravenous immunoglobulin, plasmapheresis or systemic corticosteroids (except for when given for MS relapse treatment as defined in Section 6.2.3)	Interrupt or discontinue study drug, increase vigilance regarding infections. NOTE: Restarting study drug in participants exposed to these medications is not permitted.
Administration of any live or live-attenuated vaccine (including for measles) is prohibited while participants are exposed to study drug (long lasting effects of the study drugs should be taken into consideration)	They may be administered when participants are no longer exposed to study drug. Consider risk/benefit and follow local labels.

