9.1 Discontinuation from study treatment and study

9.1.1 Discontinuation of study treatment

Discontinuation of study drug for a participant occurs when study drug is permanently stopped for any reason (prior to the planned completion of study drug administration, if any), and can be initiated by either the participant or the Investigator.

The Investigator must discontinue study treatment for a given participant if he/she believes that continuation would negatively affect the participant's well-being.

Discontinuation from study treatment is required under the following circumstances:

- Participant/guardian decision ([Section 9.2](#))
- Pregnancy ([Section 10.1.6](#) and [Section 10.1.7](#))
- Use of prohibited treatment ([Section 6.2.2](#))
- Diagnosis of PML
- Participants with active serious infections or reactivation (e.g. tuberculosis, hepatitis B or C)
- Skin and/or mucosal reactions which raise the suspicion of severe generalized major skin reactions (Stevens-Johnson syndrome, or toxic epidermal necrolysis-Lyell's syndrome)
- Hypersensitivity to the study medication
- Any situation in which continued study participation might result in a safety risk to the participant
- Protocol violation that results in a significant risk to the participant's safety
- Emergence of certain adverse events, such as malignancy (except successfully treated basal cell carcinoma, *in situ* squamous cell carcinoma and *in situ* carcinoma of cervix of uterus), liver failure or serious chronic infection (such as human immunodeficiency virus (HIV))
- Laboratory abnormalities (e.g. liver functions tests (LFTs) and abnormal test procedure defined in Appendix 1 ([Section 16.1](#)))
- Severe hypoproteinemia
- Interstitial lung disease or new onset or worsening of pulmonary symptoms, such as persistent cough and dyspnea, with or without associated fever, suspicious of interstitial lung disease
- Non-compliance with study drug or study procedures

Study treatment discontinuation should be considered under the following circumstances:

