**Table 5-5 Other reasons for exclusion from analysis**

Reason	Description	Exclusion in analyses
Site/Investigator disqualification	Due to breaches of ethical or regulatory standards, a site/investigator may be disqualified, and all data from the disqualified site will be excluded from the analysis. All data from the following site(s) will be excluded, 1003.	Exclude from Safety set and FAS
Prohibited medication (COMD02)	Data up to date of PD will be included.	Exclude from primary analyses.
Assessment performed after withdrawal of consent (WITH13)	Data up to date of PD will be included.	Exclude from applicable analyses.

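### Table 6-1 prohibits intravenous immunoglobulin and non-relapse systemic steroids without exempting uses that other protocol sections allow, and the SAP's undefined prohibited-medication code could carry the conflict into the primary analysis

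*Protocol*

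**What the plan says.** **Restrictive text.** Protocol Section 6.2.2, Table 6-1, third row, covers other immunomodulatory or disease-modifying MS treatments. It names "intravenous immunoglobulin, plasmapheresis or systemic corticosteroids", and the only exception is treatment of an MS relapse under Section 6.2.3. The action is "Interrupt or discontinue study drug, increase vigilance regarding infections", followed by the note "Restarting study drug in participants exposed to these medications is not permitted". Section 9.1.1 includes "Use of prohibited treatment" in its list of circumstances in which discontinuation of study treatment is required, with a reference to Section 6.2.2.

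**Permissive text.** Section 16.3.4 deals with IgG falling below 300 mg/dL. Study drug is to be interrupted, "Immunoglobulin substitution therapy as per local medical practice is allowed", and re-initiation may be considered once levels are normal. No route is given. Section 6.2.1 states that for the first injection "the addition of premedication with steroids (methylprednisolone 100 mg iv or equivalent) is an additional consideration". Section 6.5.3 lists an emergency or unplanned hospitalization involving excluded medications among reasons for interruption, and leaves restart to case-by-case decision.

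**SAP.** Table 5-5 has a row for prohibited medication, code COMD02. One column excludes it from the primary analyses; the other keeps data up to the deviation date. Section 2.5.2 bases the primary analysis on the FAS and imputes a missing Month 12 outcome as No. Tables 5-4 and 5-7 do not list COMD02 as a reason for leaving the FAS. Table 4-1 declares no change to the protocol's analyses.

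**The concern.** A site that reads Table 6-1 and Section 9.1.1 would stop study drug permanently in a participant given intravenous immunoglobulin for low IgG. A site that reads Section 16.3.4 could interrupt and later resume. Day 1 steroid premedication raises the same difficulty: one section offers it, and another lists the drug class as prohibited with an exception that does not cover it.

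The consequences are statistical as well as operational. Retention to Months 6 and 12 is a secondary endpoint, and SAP Section 2.7.2 derives it from study drug discontinuations. A participant who is stopped and has no valid Month 12 scan counts as a non-responder. The SAP also attaches an analysis exclusion to prohibited medication, so a code whose meaning depends on a self-contradictory list could determine how a participant enters the primary proportion.

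**Working it through.** **Step 1: the protocol sections side by side.**

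| Use | Restrictive text | Permissive text | Exempted in Table 6-1? |
|---|---|---|---|
| Immunoglobulin for low IgG | Table 6-1: intravenous form prohibited, no restart after exposure; 9.1.1: discontinuation required | 16.3.4: allowed, re-initiation possible | No |
| Day 1 intravenous methylprednisolone premedication | Table 6-1: systemic steroids prohibited except for relapse; 9.1.1 as above | 6.2.1: optional | No |
| Restart after an excluded medication | Table 6-1: barred for this row; 9.1.1 as above | 6.5.3: case by case | No |

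The third-row action also sits badly with its own note: interruption is offered, but restart is barred.

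**Step 2: the plan's own precision figures.** Half-width = 1.96 × √(p(1 − p)/n), with n = 100 (SAP Section 3):

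- p = 0.75: 1.96 × √(0.1875/100) = 8.49 points (plan: 8.5)
- p = 0.80: 1.96 × √(0.16/100) = 7.84 points (plan: 7.8)
- p = 0.85: 1.96 × √(0.1275/100) = 7.00 points (plan: 7.0)

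The stated figures reproduce.

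**Step 3: what the COMD02 row could do.** Let k of 100 participants be flagged before their Month 12 scan, and let the others respond at rate p. The documents give no value for k.

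- Reading A, flagged participants leave the denominator: estimate = p, n = 100 − k.
- Reading B, they stay in the FAS, data after the deviation are dropped and non-responder imputation applies: estimate = p(100 − k)/100, n = 100.
- Gap = p − p(100 − k)/100 = pk/100, which is p × k percentage points.

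At an assumed p = 0.80:

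| k | A: estimate (half-width) | B: estimate (half-width) | Gap |
|---|---|---|---|
| 1 | 80.0% (7.88) | 79.2% (7.96) | 0.8 |
| 5 | 80.0% (8.04) | 76.0% (8.37) | 4.0 |
| 10 | 80.0% (8.26) | 72.0% (8.80) | 8.0 |
| 20 | 80.0% (8.77) | 64.0% (9.41) | 16.0 |

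At p = 0.75 the gap is 0.75 points per flagged participant, and at p = 0.85 it is 0.85. For a use on Day 1 the deviation date would be Day 1, so under Reading B only the baseline scan would remain.

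**The case against.** The best case on the other side has four parts.

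*Purpose and timing separate the immunoglobulin uses.* The Table 6-1 row concerns MS treatments used together with study drug; Section 16.3.4 concerns replacement for low IgG during an interruption, by an unstated route. This narrows the conflict to intravenous substitution but does not remove it. The restart bar is triggered by exposure, whatever the purpose. Exclusion criterion 2c itself describes decreased IgG treated with intravenous immunoglobulin, so that route is plainly contemplated.

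*A specific permission overrides a general prohibition.* That is a sensible reading of Day 1 premedication, and SAP Section 2.4.3 identifies injection-related premedication by its own subcategory, which makes miscoding less likely. It is still an inference: no text exempts premedication from Table 6-1 or from COMD02.

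*Table 6-1 and Section 6.5.3 allow interruption.* They do, but Section 9.1.1 lists prohibited treatment among required discontinuations, and Table 6-1 bars the restart that Section 6.5.3 contemplates.

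*The link to the primary result is hypothetical.* This stands. A reader might infer that the SAP simply removes every user of a listed drug, that all participants premedicated with steroids on Day 1 would lose their Month 12 outcome, or that each would move the estimate by a full point. The documents support none of these. COMD02 is undefined, the same row keeps earlier data, and flagged participants remain in the FAS. Starting from 80/100, removing one participant gives 79/99 = 79.8% or 80/99 = 80.8%, a shift of 0.2 or 0.8 points. A full-point shift needs Reading B and a participant who would otherwise have responded; one who would not have responded shifts nothing.

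**Conclusion.** The protocol contradiction holds on the text: Table 6-1 and Section 9.1.1 cannot both be followed together with Sections 16.3.4, 6.2.1 and 6.5.3 for every participant those sections cover. For immunoglobulin this assumes intravenous substitution. It can produce opposite stop and restart decisions, and so different retention outcomes.

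The effect on the primary result is conditional. It requires that a use allowed by one section be coded COMD02, which the documents do not show. If that happened before the Month 12 scan, the choice between leaving the denominator and counting as a non-responder would be worth about 0.8 points per flagged participant at n = 100 and an assumed 80% response (0.75 to 0.85 across the plan's range of 75% to 85%). Ten flagged participants would give a gap of 8.0 points, about the size of the planned half-width of 7.8. That is an illustration, since the number affected is unknown.

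This review does not judge which clinical rule should stand.

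**What to change.** 1. **Protocol.** Reconcile Table 6-1 with Sections 6.2.1, 6.5.3, 9.1.1 and 16.3.4, so that one stated rule governs immunoglobulin substitution (including route), steroid premedication, and restart after exposure. The clinical choice is for the sponsor.
2. **SAP Table 5-5, definition.** Define COMD02 from the reconciled list, so that a use the protocol permits is never coded as a prohibited-medication deviation.
3. **SAP Table 5-5, handling.** State whether flagged participants leave the denominator or stay in the FAS under non-responder imputation. Align Section 2.5.2 and Table 5-7 with that choice, and record it in Table 4-1 if it departs from the protocol's analysis.

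The cost is a protocol clarification and a few lines in the SAP. No new data, visits or sample size are needed. If treatment has already finished, the first item becomes a record of how sites resolved the conflict; the two SAP items can still be settled before database lock.

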**Document History – Changes compared to previous final version of SAP**

Date	Time point	Reason for update	Outcome for update	Section and title impacted (Current)
30- Sep- 2020	Prior to DB lock	Creation of final version	N/A - First version	NA
04- Jul- 2023	Prior to DB lock	Incorporate protocol amendment, and dry run changes.	Amendment 1.0 approved in the documentation management system	
Section 1 Figure 1-1. Replaced with new study design as per protocol amendment.
  
Section 2.1. Site 1003 removed from analysis due to investigator disqualification.
 
Section 2.1.1.7. Added detail for the definition of the safety follow-up period.
 
Section 2.1.1.11. Added section for “discontinuation from study treatment”.
 
Section 2.1.1.12. Added section for “discontinuation from study”.
 
				
Section 2.4.2.1. Updated the visit windows.

Date	Time point	Reason for update	Outcome for update	Section and title impacted (Current)
				Section 2.8.1. Definition of treatment emergent adverse event updated.
				Section 2.8.1.3. Updated to include summary of all deaths.
				Section 2.8.2.1. Additional summary of historical change of IgG/IgM added.
				Clarification added for baseline derivation of IgG/IgM.
				[REDACTED]
				Section 2.14. Data cut-off details for interim analysis added.
				Section 4 Table 4-1. Update change to protocol specified analyses to not applicable.
				Section 5.1.3.3. Details of time imputation derivation added.
				Section 5.5. Added rule to exclude site 1003 from the analysis sets.

Date	Time point	Reason for update	Outcome for update	Section and title impacted (Current)
			General.	[REDACTED]
13-Nov-2023	Prior to DB lock	Incorporate changes from CSR dry run review	Amendment 2.0 approved in the documentation management system	
Section 2.1. Added detail to clarify the definition of core and post-treatment phases.
 
Section 2.1.1.7. Removed criteria in definition of the safety follow-up period.
 
Section 2.1.1.9. Updated the definition of the safety analysis cut-off.
 
Section 2.3.3. Tests added to summary of MS baseline characteristics.
 
Section 2.4.2. Added text clarifying presentation of by visit outputs.
 
Simplified the definition of the visit windows.
 
Section 2.4.2.2. Changed to make similar to 2301 study.
 
Section 2.5.4.1. Details of supplementary analyses provided.
 
Section 2.8.8.3. Removed vital signs analyses of pre-injection to post-injection.
 [REDACTED]

Date	Time point	Reason for update	Outcome for update	Section and title impacted (Current)
				 Section 5.1.3. Further details added to imputation rules for concomitant medications.
				 Section 5.5. Added SAS code for the MMRM analyses.
29-Jan-2024	Prior to DB lock	Incorporate changes from CSR	Amendment 3.0 approved in the documentation management system	
Section 2.1. Added text detailing post-treatment safety follow analysis.
 
Section 2.4.2.1. Added serology.
 
Section 2.4.2.2 Added Table 2-4 detailing the visit windows for morphology.
 
Section 2.5.2. Added details of other intercurrent events to align with the protocol. Added detail for the use of non-responder imputation.
 
Section 2.5.2, 2.5.4. Added clarification that assessments after the cut-off are not considered for the analysis.
 

Date	Time point	Reason for update	Outcome for update	Section and title impacted (Current)
				
Section 5.5. Added details to the description for site/investigator disqualification.
 
Included new reason of exclusion based on prohibited medication.

23-Feb-2024	Prior DB lock	Incorporate detail, and DQT meeting action.	Amendment 4.0 approved in the documentation management system	
Section 5.4.2. Added detail to TSQM-9 scoring.
 
Section 5.5. Included new reason of exclusion from analyses based on assessments performed after withdrawal of consent.

